This study will be a double-blind, randomized, placebo controlled trial, evaluating drug-free inpatients (at least 24hs period pre-admission) with depressive episode associated with past suicidal attempt and current active suicidal ideation. Patients will be randomly assigned to intranasal ketamine hydrochloride (50 mg) or saline solution (1 to 1 in both groups, suicide or suicide plus alcohol, with a total of 4 groups). After the single intranasal administration, assessments will occur at +40 min, +240 min, +24 h (phase 1), and +48 h (phase 2). For phase 2, patient may receive their regularly scheduled daily medications if improvement less than 50%. Pts will be subsequently followed up on the suicidal ideation scores until discharge once a day with treatment as usual. This study is expected to take one year to be concluded. Medication should be applied in the first 24hs after admission. There is no approved treatment for suicidal ideation and just a few trials used ketamine for suicidal ideation, none of them evaluating the intranasal route. Thus, a placebo-controlled study is warranted to prevent potential methodological issues. The use of ketamine plus standard care would bias the evaluation of the specific antisuicidal efficacy of intranasal ketamine since standard treatments in some cases may also target suicidality and mood in the short-term.

Assessment of antisuicidal efficacy will be obtained using the Columbia-Suicide Severity Rating Scale (CSSRS) as a screening tool for inclusion (based on "yes" or "no" questions) at HCPC. MADRS item 10 score of 5 or 6 suggests active suicidal risk and will be also used as the threshold for patient inclusion in the ketamine intervention. For those enrolled, the primary efficacy outcome measure will be changes in suicide severity at 24hr post-treatment based on the Scale for Suicide Ideation (SSI) scores, which assesses presence of suicidal ideation and history of suicidal behavior. Secondary outcomes to be administered at each visit include the Montgomery-Åsberg Depression Rating Scale (MADRS), the Young Mania Rating Scale (YMRS), the Clinician-Administered Dissociative States Scale (CADSS), Snaith-Hamilton Pleasure Scale (SHAPS) Alcohol Urge Questionnaire (AUQ) and the Clinician-Administered National Institutes of Health-Brief Fatigue Inventory (NIH-BFI). Inter-rater reliability will be assessed for all ratings, with accepted kappa over 0.8.

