2. Able to provide written informed consent
3. Current suicidal ideation and depressive symptoms and DSM-IV-TR depressive episode (also MADRS score $\rightarrow 12$).
4. DSM-IV-TR criteria for current alcohol abuse (but not intoxicated/withdrawal, abstinent from drinking for > 5 days prior to admission).
5. Lifetime history of suicide attempt (patient)
6. Not taking any medication in the last 24hs.
7. SSI score over 4 (first five items) and Columbia scale score 4 or 5

Exclusion Criteria:

- Unstable medical condition or medical problem with known CNS effects, e.g. uncontrolled hypertension ($SBP \geq 170$ and/or $DBP \geq 100$) or recent history (6 months) of alcohol-withdrawal seizures or significant abnormal laboratory tests (LFT 3 times higher than normal).
- Currently having a manic episode.
- Prior diagnosis of a DSM-IV-TR psychotic spectrum disorder a personality disorder or current psychotic symptoms.
- Currently under the acute effects of an illicit substance.
- Pregnant or nursing women.

As the only public-academic teaching psychiatric hospital in Houston, Texas, the University of Texas Harris County Psychiatric Center serves a large and diverse patient population. Last year, HCPC served 2443 adult psychiatric patients who had a primary diagnosis of BD (35.2% of patients served) and a similar number with MDD. More than half (52.2%) of the patients admitted to HCPC were on suicide precautions, and the mean patient length of stay was 8.8 days. We estimate being able to assess approximately 1200 patients per year ($n = 3600$) for study eligibility and recruitment.

Regarding the recruitment strategy, we will only recruit participants who seek care for suicidal thoughts or behaviors at the HCPC. Recruitment strategies will not include local advertising in any type of media. Potential participant will be seen by a treating clinician who will complete routine assessment according to standards of care for their facility. Study staff will speak with clinician in person on site in the

IRB NUMBER: HSC-MS-17-0903
IRB APPROVAL DATE: 10/09/2019

emergency department or at the research unit. Study staff will review the Inclusion/Exclusion Checklist and Study Summary. If potential participant appears eligible for study, study staff will speak with potential participant in person. Study staff will again re-review Inclusion/Exclusion Checklist with the potential participant to assess eligibility and interest in the study.

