Adequate monitoring and management of suicidal thoughts and behaviors will be critical to the safe conduct of this study. For this reason, we propose a comprehensive and multi-disciplinary approach to assess, and if necessary, treat, study participants. Monitoring for suicide risk over the course of the study will be assessed frequently through: the SSI, C-SSRS, MADRS item #10. In addition, research staff will conduct a clinical evaluation on a daily basis. During the first 4hs after the intranasal spray, inpatient research assistant-to-patient staffing ratio will be 1:1 in the first hour after treatment and in the next 3hrs a team member (PI, or MD trainee) will be with the patient and also supported by the research staff, both continuously monitoring vitals and be doing the ratings. Additionally, nursing staff and physicians are available at all hours to respond to any crisis if needed.

The following conditions would increase concern for suicidal behavior:

- SSI score of 6 or above
- C-SSRS endorsement of items #4 or #5
- MADRS item #10 score ≥ 4
- Clinical assessment of suicidal thoughts/behavior

Procedure in case of adverse events:

In addition to the nursing staff and physicians in the unit, a medical monitor will provide independent oversight of data related to subject safety. [name], Assistant Professor at the Department of Psychiatry and Behavioral Sciences, will be the independent medical monitor of the study. He will be blind to study medication, unless he believes that termination of the trial is warranted.

As a medical monitor, [name] will meet twice per year with the PI, [name], and the study team. In each meeting, the following items will be discussed:

- List and summary of adverse events.
- Whether adverse event rates are consistent with pre-study assumptions.
- Summary of recruitment and retention and reason for dropouts.
- Whether the study is on track to be completed and accomplish the stated aims.

IRB NUMBER: HSC-MS-17-0903
IRB APPROVAL DATE: 10/09/2019

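### The C-SSRS and MADRS item 10 conditions for suicide concern are already met at entry, and the SSI condition nearly always, so these cut-offs cannot show worsening over baseline

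*Combined protocol and SAP*

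**What the plan says.** The Data and Safety Monitoring section sets out how suicide risk is followed: "Monitoring for suicide risk over the course of the study will be assessed frequently through: the SSI, C-SSRS, MADRS item #10". It adds that "research staff will conduct a clinical evaluation on a daily basis". It then lists four conditions that raise concern:

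- "SSI score of 6 or above"
- "C-SSRS endorsement of items #4 or #5"
- "MADRS item #10 score ≥ 4"
- "Clinical assessment of suicidal thoughts/behavior"

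The three score conditions are absolute levels. None refers to the patient's own pre-dose rating, and no action is attached to meeting one.

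Entry is governed in two places. Inclusion criterion 7 under Study Population reads "SSI score over 4 (first five items) and Columbia scale score 4 or 5". The Design section says "MADRS item 10 score of 5 or 6 suggests active suicidal risk and will be also used as the threshold for patient inclusion"; this threshold does not appear in the numbered inclusion list.

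Separately, Study Procedures withdraws a patient whose condition becomes significantly worse in the clinicians' judgment, and schedules ratings at baseline, 40 and 240 minutes, day 1 and day 2.

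**The concern.** The trial enrolls patients because their suicidality ratings are high. A monitoring cut-off at or below the entry level describes who was admitted. It cannot mark a patient whose rating rises after study drug. If the score conditions are met on arrival, they read the same for a patient who is unchanged and for one who has become worse.

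At stake is the safety description of a single-dose drug trial in acutely suicidal inpatients. The plan collects the ratings needed to show how many patients worsened in each arm, but it nowhere asks for that count:

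- The Statistics section covers presence or absence of ideation and behavior, severity scores, and change over time.
- The medical monitor's agenda covers adverse events, recruitment, retention and dropouts.
- The early holding rule uses overall SSI improvement below 20% in the first 15 patients, and an overall figure can conceal individual worsening.

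**Working it through.** The plan gives no figure to reproduce here. The check sets the entry thresholds beside the listed conditions.

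| Scale | Needed for entry | Condition for concern | Already met at entry? |
|---|---|---|---|
| C-SSRS | 4 or 5 (Inclusion Criteria, item 7) | item 4 or 5 endorsed | Always |
| MADRS item 10 | 5 or 6 (Design) | 4 or more | Always, since 5 > 4 |
| SSI | over 4 on the first five items, so 5 or more in whole points (item 7) | 6 or more; total or first five items not stated | Yes, unless exactly 5 |

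**SSI.** If the condition refers to the total, then total = first five + remaining items ≥ 5 + 0 = 5. The condition fails only when the first five items sum to 5 and the rest to 0. If it refers to the first five items only, 5 is unflagged and 6 to 10 are flagged.

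**Enumeration.** Assumptions not in the documents: whole-number scores, the first five SSI items summing to at most 10, and the remaining SSI items taking values 0 to 28. The condition is read on the total.

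- Entry-admissible score sets: 6 (first five SSI, 5 to 10) × 29 (remaining SSI, 0 to 28) × 2 (C-SSRS, 4 or 5) × 2 (MADRS item 10, 5 or 6) = 696.
- Sets meeting both the C-SSRS and MADRS conditions: 696 of 696.
- Sets missing the SSI condition: 1 × 1 × 2 × 2 = 4, so 696 − 4 = 692 meet all three.

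These count score combinations, not patients. The range assumed for the remaining SSI items changes the totals but not the conclusion.

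**Sensitivity to which entry threshold is enforced.**

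- Drop the MADRS threshold because it is outside the numbered list, letting item 10 run from 0 to 6: 6 × 29 × 2 × 7 = 2,436 sets, all meeting at least one condition through C-SSRS.
- Drop the C-SSRS threshold instead, letting it run from 0 to 5: 6 × 29 × 6 × 2 = 2,088 sets, all meeting at least one condition through MADRS.

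**What a rise does to the conditions.** C-SSRS from 4 to 5 leaves its condition unchanged. So does MADRS item 10 from 5 to 6, and so does any rise in SSI from 6 upward. The one rise from an entry score that changes a condition is SSI from 5 to 6 or more.

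**The case against.** The strongest reply is that the list does not set out to detect drug-induced worsening. It applies throughout the study, triggers nothing, and answers whether a patient is at risk now; absolute levels suit that question, and it is coherent to enroll high-risk patients and regard them as high-risk. Change is also handled elsewhere: the primary outcome is change in SSI at 24 hours, random effects models follow scores over time, patients are under suicide watch and observed closely for four hours, and withdrawal for worsening is deliberately left to clinicians.

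Much of this stands, and it rules out several stronger readings that a reader might infer.

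- That the monitoring plan cannot show worsening. The fourth condition, the daily evaluation and the withdrawal rule can all register it. The limitation belongs to the score cut-offs.
- That the score conditions carry no information. Falling below a cut-off shows improvement, and returning above it shows relapse. Neither shows worsening beyond baseline.
- That SSI can rise from its lowest qualifying value to its maximum with no condition changing. A patient entering at exactly 5 does newly cross the SSI cut-off.
- That the medical monitor is left unable to compare arms. The monitor is blind unless termination seems warranted, and is not asked to make that comparison.
- That post-dose C-SSRS endorsement merely repeats the screening answer. The screening version looks back over lifetime and six months, while the follow-up version covers the time since the last assessment. A qualifying screening score need not describe the moment of dosing, so a pre-dose reference needs to be stated.

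The reply does not restore the score cut-offs as a signal of worsening. Nor do the planned analyses of average change count the individuals who became worse in each arm.

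**Conclusion.** The point holds for the three score conditions. With both entry thresholds in force, every eligible patient meets at least two of the three at entry, and all three unless the SSI score is exactly 5. If only one of the C-SSRS and MADRS thresholds is enforced, every patient still meets at least one. The C-SSRS and MADRS cut-offs therefore cannot separate worsening over baseline from the entry state, and the SSI cut-off can do so only for a patient entering at 5. Detection of worsening rests on clinical judgment, which the plan does provide.

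This assumes whole-number scores and that entry criteria are applied as written. It is a gap in clarity and in safety reporting. It does not show that patients are unmonitored, and it does not touch the primary analysis. The remedy is cheap enough that it should be made.

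**What to change.** 1. Reconcile the Design section, inclusion criterion 7, the withdrawal rule in Study Procedures and the list under Data and Safety Monitoring. State which SSI score the list means, whether the MADRS item 10 threshold is an inclusion criterion, and what the list is meant to signal in patients who nearly all enter at or above its score levels. Any clinical threshold is for the investigators to set.

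2. Add a descriptive safety table to the final report: change from each patient's own pre-dose SSI, C-SSRS and MADRS item 10, including the number with any increase, by arm at 40 min, 240 min, 24 h and 48 h. Any increase is a reporting category here and not a rule for managing patients. State the pre-dose C-SSRS reference and its look-back period. The rating schedule names symptom domains rather than scales, so show C-SSRS at the times when it is actually rated.

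3. During the trial, give the medical monitor this table pooled over arms, or in another form that keeps the blind.

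The cost is one amended paragraph and one table from ratings already planned. The downside is small counts, so the table should be read descriptively.

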Since there is no available studies in this field using the intranasal route and considering that the highest risk times for suicidal behavior are the week after admission to an inpatient psychiatric unit and the week after discharge (Qin & Nordentoft 2005), we aim to investigate the rapid antisuicidal effects of intranasal ketamine in patients with suicidal ideation during depressive episodes with or without recent use of alcohol. We hypothesize that a single dose of intranasal ketamine will induce a rapid, robust and sustained decrease in suicidal ideation in subjects with a comorbid major depressive episode and alcohol dependence relative to only depression and placebo as defined by changes in suicidal ideation scales after 24hrs.

Objectives

Primary objective: To evaluate the rapid antisuicidal effects on a single dose of intranasal ketamine (50mg) in a sample of depression comorbid or not with alcohol abuse compared to placebo.

Secondary objectives:

- To identify clinical variables and dimensions associated with the potential antisuicidal efficacy of intranasal ketamine.
- To identify post-treatment biomarkers associated with the antisuicidal response to ketamine.
- To evaluate the role of recent alcohol abuse in the antisuicidal and antidepressant effects of ketamine
- To identify clinical and biological predictors of response to ketamine
- To evaluate safety and tolerability of intranasal ketamine

Hypothesis:

-Primary: A single dose of ketamine will induce a rapid, robust and sustained decrease in suicidal ideation in subjects with a comorbid major depressive episode and alcohol dependence relative to placebo as defined by change in SSI scale after 24hrs.

-Secondary:

- The antisuicidal efficacy of intranasal ketamine will be independent from its rapid antidepressant efficacy.
- Intranasal ketamine will present superior antisuicidal efficacy in the group with comorbid depression and alcohol compared to depression only.
- Antisuicidal response to ketamine will be correlated with changes in neurotrophic factors and inflammatory markers at one day after ketamine infusion. -Intranasal ketamine (50mg) will be safe and well-tolerated.
- Alcohol use and/or family history of alcohol abuse will be associated with better antisuicidal and antidepressants response to ketamine.

IRB NUMBER: HSC-MS-17-0903

IRB APPROVAL DATE: 10/09/2019

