Description of Study Populations: A total of 60 individuals (males and females) between the ages of 21-60 will be enrolled in the study. Two participant populations will be recruited into this protocol. Participant populations are individuals with the following conditions: 1.) current suicidal ideation and past suicide attempt under intranasal ketamine (Group 1, n= 30) and current suicidal ideation and past/recent suicide attempt under placebo (Group 2, n= 15). Group 1 will include two subgroups, with (n=15) or without (n=15) recent abuse of alcohol plus positive personal/family history for alcoholism. The study will take place at a Research Unit at the Harris County Psychiatric Center, UT Houston. Participants at acute risk will be admitted to the HCPC 2D Unit, a secure, but voluntary psychiatric unit, in which there will be nursing staff and physicians available at all hours to respond to any crisis as needed. Subjects will complete an informed consent process and will be systematically screened for inclusion and exclusion criteria. Only participants with a lifetime history of suicide attempt will be enrolled.

Design

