Potential psychotomimetic, dissociative, hemodynamic, and general adverse effects associated with ketamine will be also measured. Safety and tolerability will be specifically assessed the Clinician-Administered Dissociative States Scale (CADSS) and the mood item of the Young Mania Rating

IRB NUMBER: HSC-MS-17-0903
IRB APPROVAL DATE: 10/09/2019

Scale (YMRS). Clinically significant changes will be characterized as systolic or diastolic blood pressure (BP) >180/100 mmHg or heart rate >110 beats/minute.

Clinician Administered Measures

- 1) The *Scale for Suicide Ideation* (SSI) is a 21-item clinician-administered scale designed to quantify the intensity of current conscious suicidal ideation in various dimensions of self-destructive thoughts or wishes: the extent of the wish to die, the desire to make an actual suicide attempt, and details of any plans; also, internal deterrents to an active attempt, and subjective feelings of control and/or courage regarding a proposed attempt. Individuals are asked to report their current and worst-point suicidal thoughts (Beck et al 1979).
- 2) The *Columbia Suicide Severity Rating Scale* (C-SSRS) is a widely used measure of suicidal ideation and behavior. The “Screening/Baseline” version of the measure evaluates suicidal ideation and behavior both lifetime and in the last six months. The “Since Last Visit” version assesses suicidal thoughts and behavior since the last assessment. The C-SSRS takes 15 minutes to administer (Posner et al 2011).
- 3) Montgomery-Asberg Depression Rating Scale (MADRS) is a widely-used ten item instrument evaluating depressive symptoms in adults. The estimated time to completion is 20 minutes. Interrater reliability is high and scores correlate significantly with those of other validated depression measure, e.g. HDRS. Each of the ten items is rated on a scale of 0-to-6, with differing anchors describing escalating psychiatric severity (Montgomery et al 1979).
- 4) *Young Mania Rating Scale* (YMRS) consists of 11 items used to assess hypomanic/manic symptoms. The time for administration is 15-30 minutes (Young et al 1978).

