Our outcome analyses will focus on examining the acute effects and duration of intranasal ketamine treatment during inpatient psychiatric hospitalization. As a primary outcome, we will examine the efficacy of intranasal ketamine for preventing suicidal behavior and ideation among adult patients in a current depressive episode at day 1. Our primary outcome analysis seeks to answer two questions: 1) will intranasal ketamine work acutely compared to placebo, and 2) how long will this effect persist? Effect sizes will be calculated for intranasal ketamine treatment. In the primary outcome analysis, two dichotomous primary outcome measures will be examined in the evaluation: 1) the presence or absence of suicidal ideation, and 2) the presence or absence of suicidal behavior as measured using the C-SSRS and SSI. Our secondary outcome analysis will include an examination of 1) the effects of intranasal ketamine for suicidal ideation while controlling for improvements in depression and other dimensions 2) the potential role of recent alcohol abuse and previous alcohol dependence in the rapid anti-suicidal effects of intranasal ketamine. The symptom severity ratings of SSI, the C-SSRS total score and, as well as changes in MADRS scores will be utilized as primary and secondary outcomes, respectively. Normality assumptions for continuous variables will be examined. Baseline characteristics will be compared between responders and non-responders with the Mann-Whitney U test for continuous variables and the chi-square test for categorical variables. Changes between two time-points for continuous variables were tested with paired t tests, and associations between continuous variables will be quantified with the Spearman correlation coefficient. Random effects models will be performed to quantify changes in clinical score and its component items over time and to compare temporal differences between eventual responders and non-responders.

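### The primary outcome is contradictory: one continuous SSI measure in the Hypothesis and Design sections, several primaries in Statistics, and no rule for what counts as success

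*Combined protocol and SAP*

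**What the plan says.** **Outcome.** In Design, "the primary efficacy outcome measure will be changes in suicide severity at 24hr post-treatment based on the Scale for Suicide Ideation (SSI) scores". The primary hypothesis agrees on the measure: an effect "in subjects with a comorbid major depressive episode and alcohol dependence relative to placebo as defined by change in SSI scale after 24hrs". The Statistics section differs: "two dichotomous primary outcome measures will be examined in the evaluation: 1) the presence or absence of suicidal ideation", the second being presence or absence of suicidal behaviour, with the C-SSRS and the SSI both named as the source. The same paragraph later lists SSI severity, the C-SSRS total and MADRS change as primary and secondary outcomes respectively. That makes SSI severity primary and leaves the C-SSRS total unclear. It also puts the question of how long the effect lasts inside the primary analysis.

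**Population.** The primary objective is set "in a sample of depression comorbid or not with alcohol abuse compared to placebo", whereas the primary hypothesis is confined to comorbid patients. Statistics speaks of adults in a depressive episode and treats the role of alcohol as secondary. Inclusion criterion 4, under Study Population, lists current alcohol abuse without qualification.

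**Decision rule.** Statistics sets two-sided alpha at 0.05 for all tests. Frequentist and Bayesian analyses run in parallel, and potential confounders lead to analyses with and without adjustment. No section gives a hierarchy, an alpha split, a co-primary rule or a decisive analysis.

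**The concern.** A reader holding the unblinded data could defend SSI change, absence of ideation, or the result in comorbid patients as the primary result, each from the current text. The same data could then be called positive or negative depending on the section followed.

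The dichotomous outcomes are themselves open. For ideation, two scales are named, with no SSI value that means absent and no rule for disagreement between them. For behaviour, every enrolled patient has a lifetime suicide attempt, so a lifetime reading would not vary; only new events can discriminate. The C-SSRS can supply these, since its follow-up "version assesses suicidal thoughts and behavior since the last assessment". But the count would cover one day in inpatients on active suicide watch (Potential Benefits), and no event rate is given.

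At stake are the false-positive rate if any one primary may count, and the chance of success if all must.

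**Working it through.** **1. The plan's own figure.** Statistics gives 11 per group from 60% v 10% response, power 0.8, two-sided 0.05. The unpooled formula reproduces it: (1.960 + 0.842)² × (0.6×0.4 + 0.1×0.9) / 0.5² = 10.36, rounded up to 11. (The pooled formula gives 14.) These are response rates from depression studies, so the figure does not show which suicidality outcome decides. The other planning figure, d = 0.7, is a standardised mean difference and fits a continuous SSI score.

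**2. Arm sizes.** The documents conflict, so both readings are carried. A total of 60 allocated "1 to 1 in both groups, suicide or suicide plus alcohol, with a total of 4 groups" gives 30/30. Group 1 with n = 30 against "current suicidal ideation and past/recent suicide attempt under placebo (Group 2, n= 15") gives 30/15.

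**3. Either SSI change or ideation may count.** Independent tests would give 1 − 0.95² = 9.75%. The outcomes overlap, so null trials were simulated (20,000 per setting): normal scores, ideation defined by a cut-off on the 24-hour SSI, t test on change. The documents give none of the inputs. Assumed: baseline to 24-hour correlation 0-0.7, ideation at 24 hours 30-70%, baseline SD 0.3-1 times the 24-hour SD, all randomised patients analysed. The SD ratio is varied because the minimum SSI at entry may narrow the baseline spread. Result across both allocations: about 6-8% with Fisher's test, 7-10% with uncorrected chi-square. No test is named for these outcomes; chi-square appears only for comparing responders with non-responders.

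**4. SSI change may count in all patients or in comorbid patients only.** With half the patients comorbid, the two test statistics correlate at about √(30/60) = 0.71. Two normal statistics with correlation 0.7 give 8.4% for at least one rejection. Simulated t tests give about 8.3-8.6%.

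**5. All must succeed.** When neither SSI nor ideation responds, both reject in about 0.3-2% of trials. If one truly responds and the other does not, the error approaches the size of the remaining test, about 3-5%. The general bound is therefore about 5%.

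**6. Power for new suicidal behaviour.** Assume zero ketamine events, the most favourable case. Significance then needs 6/30 or 3/15 placebo events with Fisher (p = 0.024, 0.032), or 4/30 or 2/15 with chi-square (p = 0.038, 0.041). Power is the binomial chance of reaching that count. For example, with chi-square at 30/15 and a 5% rate: 1 − 0.95¹⁵ − 15 × 0.05 × 0.95¹⁴ = 17.1%.

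| Assumed placebo rate | Power across tests and allocations |
|---|---|
| 2% | 0-4% |
| 5% | 0.3-17% |
| 10% | 7-45% |
| 20% | 57-88% |

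**7. Power for SSI change at d = 0.7** (on the analysed score). The noncentrality is 0.7 / √(1/n₁ + 1/n₂), two-sided 0.05.

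| Arms | Noncentrality | Power |
|---|---|---|
| 30/30 | 2.71 | 76% |
| 30/15 | 2.21 | 58% |
| 15/15 (comorbid only) | 1.92 | 46% |
| 15/8 or 15/7 (comorbid only, 15 placebo patients split evenly) | 1.60 or 1.53 | 33% or 31% |
| 11/11 | 1.64 | 35% |

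Reaching 0.8 at 1:1 would take 2 × (1.960 + 0.842)² / 0.7² = 32.04, so 33 per arm by the normal approximation.

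**The case against.** The best defence is that SSI change at 24 hours is plainly intended. It is primary in Hypothesis and Design, SSI severity is listed again in Statistics, the early holding rule uses SSI scores, and d = 0.7 fits it. That stands, so the outcome is contradictory rather than undefined. It does not cure the conflict, because the section that governs the analysis expressly gives primary status to other outcomes.

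On population, the objective and Statistics cover all patients, and alcohol's role is secondary elsewhere. One hypothesis sentence conflicts, and so does criterion 4, which read literally requires current alcohol abuse in everyone. Naming all randomised patients therefore does not settle the population until that criterion is reconciled.

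The two covariate sets are offered as a check on confounding, which is reasonable; what is missing is which one decides.

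Two stronger readings are tempting. A reader might infer that alpha is inflated whatever rule applies. The documents do not support that: no rule is stated, and an all-must-succeed rule keeps error at or below about 5%. A reader might also infer that such a rule always holds error well below 5%. That is true only when no outcome responds.

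**Conclusion.** The contradiction is established from the text alone and must be fixed before unblinding. Its size depends on a rule that the plan does not state. If either SSI change or ideation may count, the false-positive rate is about 6-10% across tests. If SSI change may count in either population, it is about 8.3-8.6%. If all must succeed, error is controlled, but success is unlikely unless suicidal behaviour is common on placebo: even at an assumed 10% rate with no ketamine events, power for that outcome is 7-45%.

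The error rates rest on the assumed correlation, prevalence and SD ratio, and the behaviour figures on assumed event rates. The SSI power figures rest only on d = 0.7 and the two arm-size readings, except that the smallest comorbid arms also assume an even placebo split.

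**What to change.** - In Statistics, make change in SSI at 24 hours (current rating, not worst-point), ketamine v placebo, the single primary outcome.
- Take all randomised patients as the population, in line with the primary objective and Statistics. Reword the primary hypothesis to match and keep the comorbid group secondary. Reconcile inclusion criterion 4 with Objectives, Description of Study Populations and Design, which describe patients with and without alcohol abuse.
- Name one Frequentist analysis as decisive, with its covariates fixed in advance. Label the Bayesian and alternative-covariate analyses supportive.
- Make ideation yes/no (one scale, one rule), persistence and the C-SSRS total secondary outcomes tested in a stated order, or call them exploratory. Report behaviour descriptively.
- Restate power for this primary: 76% (30/30) or 58% (30/15) at d = 0.7, below the stated 0.8. Say that 11 per group does not apply to it (35% power).

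**Cost.** Success can no longer be claimed on a dichotomous outcome or in the comorbid group alone, and the stated power becomes less favourable. No new data or patients are needed. Keeping the comorbid-only hypothesis as primary is possible, but power would be 31-46%.
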